This is a 6-year, 5-site, randomized behavioral efficacy trial of 600 participants with the MetS. Trial coordination is conducted by a research coordinating unit (RCU) and an intervention coordinating unit (ICU), located within the Department of Preventive Medicine at Rush University Medical Center in Chicago. Patients with MetS who are motivated to manage it by changing their lifestyle, and do not have any medical contraindications or logistical barriers, are recruited serially from each of the 5 participating clinical centers over 4 waves of 6-month recruitment periods. Each site is expected to recruit 30 participants/wave, and 120 participants over all 4 waves, to achieve a total of 600 participants in the trial. Recruitment proceeds in 3 steps to confirm medical, behavioral, and logistical eligibility. Once a site has recruited 30 participants, they are randomized in a ratio of 1:1 to the Group-based or Self-Directed arm. Randomization is stratified by site in permuted blocks. Outcome evaluation is conducted at baseline, at the end of the intensive phase of the intervention at approximately 6 months, halfway through the maintenance period at approximately 15 months, and at the end of follow-up at approximately 24 months. **Figure 1** presents the trial design. **Figure 2** presents the timeline for the 6-year trial including the set-up, serial recruitment in 4 waves, intervention, and maintenance. This revised trial timeline reflects a 4-5 month suspension of in-person visits due to the Covid-19 pandemic.

[figure not shown]

Figure 1. Trial design

[figure not shown]

Figure 2. Trial timeline

EQUIPOISE AND BLINDING

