Component 2 (Run-In Period). A Run-In period was developed to identify those who are willing and able to engage in a selected set of activities required by the Group-Based program. This Run-In includes successful completion of the accelerometer protocol (wear accelerometer for 7 consecutive days, 10 hours/day), food and beverage logs (record all food and beverage intake over an entire day for a minimum of 3 weekdays and 1 weekend day), and completion of a worksheet that outlines a logistical plan for how to access vegetables and a location for physical activity (completed at home or during Visit B).

Component 3 (Visit B). The second in-person visit includes a 12-hour fasting blood draw, physical measures, confirmation that the Run-In protocol was completed successfully, and completion of baseline questionnaires. Visit B occurs within 1 month of randomization. At the conclusion of Visit B, prospective participants are asked about continued interest, informed of expected wait time until the start of the program, and entered into the recruitment waiting protocol where they are kept informed of likely dates of starting treatment in ongoing contacts every 2 weeks. If a prospective participant is ineligible based on metabolic syndrome criteria or needs medical clearance for trial participation, the research assistant will follow-up with a phone call.

Randomization

Randomization is conducted by the RCU in permuted blocks and stratified by site. Since 1 of the arms in the trial is a group-based treatment of 15 participants/group, randomization will occur when 30 prospective participants are confirmed to be eligible and interested. Treatment should begin immediately after randomization. Upon randomization, participants are informed of the arm to which they were randomized by a mailed letter, an email, and a follow-up phone call from the respective site interventionist.

As randomization progresses, key population descriptors are compared in the trial arms to ensure that randomization is successfully balancing arms on key baseline characteristics. If any key covariate, such as age, race, gender, employment status, weight, or MetS component, differs by treatment arm, additional stratification in the randomization scheme is considered.

INTERVENTIONS

Highly motivated participants are recruited to help determine the better and more cost-effective way to encourage sustained lifestyle change to reverse the MetS.

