Vital Status, Adverse Events, Co-Interventions	3, PII, 9, 12, MM, 18, 21, EoT	RA
Contact Info	B,3, PII, 9, 12, MM, 18, 21, EoT	RA
Five-Facet Mindfulness Questionnaire	B, PII, MM, EoT	RA
Eating Competence Questionnaire	B, PII, MM, EoT	RA
Demographics	B, PII, MM, EoT	RA
Labs (Lipid Panel, Glucose and A1c)	B, PII, MM, EoT	RA
Medical History	B, PII, MM, EoT	RA
NCI's Fruit and Vegetable Screener	B, PII, MM, EoT	RA
Food Log and Logistic Plan	B	RA
Perceived Stress Scale	B, PII, MM, EoT	RA
Depression: Patient Health Questionnaire (PHQ-8)	B, PII, MM, EoT	RA
Physical Measures (BP, HR, Waist, Weight, Height)	B, PII, MM, EoT	RA
Automatic Habits: Self-Report Habit Index	B, PII, MM, EoT	RA
Social Support for Diet and Exercise	B, PII, MM, EoT	RA
Sugar-Sweetened Beverage Intake	B, PII, MM, EoT	RA
Visit log	B, PII, MM, EoT	RA
Quality of Life: Short Form Health Survey (SF-36)	B, PII, MM, EoT	RA
Contacts with Health Network	B, PII, MM, EoT	RA
Prescription Medications	B, PII, MM, EoT	RA
MacArthur Ladder of Subjective Social Standing	B	PPT
USDA Food Security	B	RA
Treatment Credibility Questionnaire	B	PPT
Patient Preference for Each Treatment	B	RA
Program Satisfaction	EoT	PPT
Substance Use/Abuse - WHO ASSIST	B	RA

Montreal Cognitive Assessment	B	RA (if needed)
-------------------------------	---	----------------

Change of Status

The trial status of a participant refers to their level of participation in the trial. A *Participant Status Form* is completed whenever a status change occurs. All efforts are made to collect data on the primary outcome (MetS at 2 years), at the very least.

Lost-to-Follow-Up. A participant is considered “lost-to-follow-up” after missing two consecutive trial contacts without responding to messages, texts, or other forms of communication. Staff exhausts all avenues to locate the participant, including telephoning at least 10 times on different days, at varying times of day, contacting secondary contacts and the last medical provider on record, and checking online to identify new contact information. Failure of these attempts triggers a registered letter sent to the participant’s most recent address, to which non-response confirms the status as “lost-to-follow-up.”

Withdrawal from the Intervention. This status applies to a participant who no longer wants to participate in any intervention activities, but is willing to continue completing follow-up visits.

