Consideration must be given to the fact that the proposed trial employs a “partially clustered” design where clustering is present in only 1 of the 2 arms. The Group-Based Program is delivered to participants in groups, or clusters, of approximately 15 participants. Connection and interactivity within each of these “experimentally-induced” clusters is a key component. The intraclass correlation coefficient (ICC) measures the extent to which participant responses are influenced by the cluster to which they belong. Since this clustering feature is present in only one of the two arms, its effect is muted. Results from our previous studies are consistent with those of others [13-14] indicating that the ICC could reasonably range from 0.01 to 0.20. We conservatively assume an ICC of 0.15 and adjust the total sample size required to achieve 85% power to 286 per arm or a total sample size of 572. We adjust upward to 300 participants/arm, a total sample size of 600 participants, 120 participants at each of 5 clinical sites, and 8 intervention clusters per site.

ANALYSIS PLAN

Analyses will be performed using an intent-to-treat approach that includes all patients as randomized, regardless of treatment dose. All analyses will use two-sided tests conducted at $\alpha=0.05$. Basic summary statistics will be based upon cluster-adjusted chi-square tests and t-tests. If a distribution is non-normal, cluster-adjusted

Wilcoxon rank sum tests will be used. Supplemental analyses will include mixed effects regression models to account for cluster effects and control for important covariates. The impact of missing data will be evaluated using sensitivity analyses. If data are missing at random, multiple imputation will be employed. If data are not missing at random, an appropriate statistical model will be employed (e.g. a pattern mixture model with sensitivity analyses).

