The primary hypothesis is achievement of a clinically significant MetS remission at 24 months in $\geq 40\%$ of the participants in the Group-Based program and $\leq 20\%$ of the participants in the Self-Directed program. Achieved rates will be observed, relative to these benchmarks, without statistical support. The primary statistical analysis will compare MetS remission at 24 months between the trial arms using a cluster-adjusted chi-square test. A secondary analysis will compare these rates using a mixed effects logistic regression model examining treatment over time (i.e., baseline through 24 months), a treatment*time interaction, and adjustments for age, gender, race/ethnicity, socioeconomic status, geographic site, BMI, number of co-morbidities, and number of MetS components. Random effects (e.g. random intercept, time, intervention cluster) will be included in the model only if they significantly improve model fit as determined by the likelihood ratio test.

Behavioral treatment targets will be compared by arm, without statistical support, as the proportion of participants achieving clinically significant goals (as presented in the hypothesized pathway in **Figure 3**), based upon the pre-determined benchmarks. Statistical support will be provided by a cluster-adjusted chi-square test. All other secondary and exploratory outcomes will be compared using the relevant cluster-adjusted t-test or chi square test. These comparisons will be conducted using data from post-intensive intervention, mid-maintenance, and end-of-treatment visits and trends over time will be examined. Supplementary analyses will use generalized linear mixed effects modeling, with a behavioral treatment target or weight as the outcome, treatment group as the primary predictor, random effects to account for time, site, and cluster, and selected covariates.

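### Efficiency, low severity: continuous secondary outcomes have no baseline covariate in the main comparison, and the primary test leaves out site, the randomisation stratum

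*Combined protocol and SAP*

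**What the plan says.** **Randomisation.** Trial Design: "Randomization is stratified by site in permuted blocks". The Randomization section repeats this ("Randomization is conducted by the RCU in permuted blocks and stratified by site") and adds that, if arms drift apart on a key covariate, "additional stratification in the randomization scheme is considered".

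**Primary test.** Analysis Plan: "The primary statistical analysis will compare MetS remission at 24 months between the trial arms using a cluster-adjusted chi-square test". No site term is named. In the Sample Size section a cluster is an intervention group of about 15 in the Group-Based arm, so cluster adjustment does not bring site in.

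**Other outcomes.** "All other secondary and exploratory outcomes will be compared using the relevant cluster-adjusted t-test or chi square test". The Analysis Plan substitutes cluster-adjusted Wilcoxon tests for non-normal data. It does not say whether follow-up values or changes are compared. Table 2 schedules A1c, physical measures, perceived stress, PHQ-8 and SF-36 at baseline and at every in-person follow-up visit.

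**Where site and covariates do appear.** A secondary mixed logistic model for remission adjusts for site, BMI and number of MetS components, among others. Supplementary mixed models with random effects for time, site and cluster, plus unlisted covariates, are stated for a behavioural target or weight. A general sentence adds: "Supplemental analyses will include mixed effects regression models to account for cluster effects and control for important covariates". Those covariates are not named.

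**The secondary remission model** is described as "examining treatment over time (i.e., baseline through 24 months". Its random effects, including intervention cluster, stay only if a likelihood ratio test shows better fit.

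**The concern.** A main analysis normally reflects the factor used to stratify randomisation and uses a baseline value that is already collected. Here the main comparisons do neither.

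With 1:1 allocation within site, site differences shared by both arms cancel in the treatment difference. They remain in a standard error computed as if site did not exist, so that standard error is too wide when sites differ.

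For continuous secondary outcomes, leaving out the baseline value gives wider intervals than necessary. The choice between follow-up values and change scores is also left open until the data are seen. At stake is precision, mainly for secondary outcomes.

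The secondary remission model raises a different matter, one of validity. A rule that can drop the cluster effect may treat grouped participants as independent. A baseline visit at which nobody can be in remission carries no information on treatment.

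**Working it through.** **Inputs from the documents.** Remission 40% vs 20%, two-sided 0.05, power 85%, ICC 0.15, groups of about 15, 300 per arm, 5 sites, 20% loss.

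**The plan's own figure first.** n = [1.960·√(2·0.30·0.70) + 1.036·√(0.24 + 0.16)]² / 0.20² = 92.7, so 93 per arm. Then 93/0.8 = 116.25, so 117, which is the stated figure. Loss is therefore built in, and 300 × 0.8 = 240 per arm is the evaluable number.

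**Groups.** 300/15 = 20 groups, 4 per site, each with 15 × 0.8 = 12 evaluable. Sample Size says 8 clusters per site, but 60 Group-Based participants per site in groups of 15 give 4. A variant with 8 groups of 6 per site is reported below.

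**1. Continuous secondary outcomes.** Assumed: outcome SD 1, no clustering at baseline (groups are formed by randomisation), no site effect, baseline correlation r = 0.3 / 0.5 / 0.7 (none is given). Variance of the arm difference × 240:

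- Follow-up values: 12·0.15 + 0.85 + 1 = 3.65
- Change scores: 3.65 + 2(1 − 2r) = 4.45 / 3.65 / 2.85
- Baseline-adjusted: 3.65 − 2r² = 3.47 / 3.15 / 2.67

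Reduction against follow-up values: 5 / 14 / 27%. Against change scores: 22 / 14 / 6%. The difference detectable at 85% power, (1.960 + 1.036)·√(variance), is 0.37 SD for follow-up values at any r, 0.41 / 0.37 / 0.33 SD for change scores, and 0.36 / 0.34 / 0.32 SD adjusted.

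**2. Primary test.** 40,000 simulated trials per setting; logit-normal site effect in both arms and group effect in the Group-Based arm only; average rates held at 40% and 20% (20% in both arms for type I error). Unstratified variance: variance of the 20 group proportions / 20, plus binomial variance in the Self-Directed arm. Stratified: the same quantities within site, averaged over sites. Satterthwaite df. The site SD is assumed, with total ICC held near 0.16.

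| Site SD (logit) | Type I error %, unstratified / stratified | Power %, unstratified / stratified | Mean SE, unstratified / stratified |
|---|---|---|---|
| 0 | 5.5 / 5.5 | 92.8 / 92.3 | 0.0580 / 0.0578 |
| 0.15 | 5.1 / 5.2 | 92.8 / 92.5 | 0.0579 / 0.0574 |
| 0.3 | 4.8 / 5.4 | 93.1 / 93.3 | 0.0576 / 0.0561 |
| 0.5 | 4.3 / 5.4 | 94.5 / 95.8 | 0.0569 / 0.0527 |
| 0.7 | 3.3 / 5.4 | 95.3 / 97.8 | 0.0564 / 0.0481 |

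The last row is extreme: Group-Based site rates of 25 to 55% within one SD of the mean. The nominal power change runs from 92.3 − 92.8 = −0.5 to 97.8 − 95.3 = +2.5 points. With both tests set to exactly 5% size, power is 92.2 / 92.7 / 93.4 / 95.5 / 97.2% unstratified and 91.5 / 92.2 / 92.8 / 95.5 / 97.7% stratified, a difference of less than 1 point either way.

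Sensitivity:

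- Site variance added on top of the full group effect: 92.1 vs 93.5% at site SD 0.5, and 90.0 vs 94.7% at 0.8 (about +5 points).
- The least favourable version tried: no loss to follow-up, fixed df of 19 and 15, average rates not re-centred. At SD 0.8, power is 83.4 vs 91.6% and type I error 2.1 vs 4.2%.
- 8 groups of 6 per site: power 98.1–98.9% vs 98.1–99.4%; unstratified type I error falls from 5.2 to 3.7%.

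**3. Secondary remission model.** Entry requires at least 3 components (Eligibility) and remission means fewer than 3 (Sample Size), so remission at baseline is zero in both arms by design. For the likelihood ratio rule: one-visit normal approximation, 20 groups of 12 vs 240, cut-offs 2.71 and 3.84, 200,000 draws per ICC. Type I error is 5.4–5.5% at ICC 0.01, 6.3–6.8% at 0.05, 5.8–6.2% at 0.10, 5.3–5.5% at 0.15 and 5.1–5.2% at 0.20, against 5.0–5.1% if the cluster effect always stays. At ICC 0.05 the rule drops it in 62–71% of trials. The planned model is logistic over several visits, so these figures are indicative only.

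**The case against.** The best defence is that the primary test is simple, pre-specified and at worst conservative. At equal size a site term gains almost nothing, and if sites do not differ it costs about 0.5 points of nominal power. The stratified test itself runs at about 5.2 to 5.5%, slightly above nominal. All of this stands, and it is why the primary-test part ranks low.

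It is also fair to say that site and covariates are in the plan, so the question is largely which analysis comes first. That holds for remission, behavioural targets and weight. It does not hold for A1c, BMI, perceived stress, depressive symptoms or vitality, for which only the general sentence with unnamed covariates applies.

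The Wilcoxon route weakens the t-test argument for skewed scales. PHQ-8 is a likely case, since scores of 10 or more are excluded at entry. Weight lost in kg is already a change from baseline, so the point is weaker there too.

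A reader might infer that ignoring the stratum invalidates the primary test or inflates its error rate. The documents do not support that: allocation is 1:1 within site, and omitting site moved type I error downwards as site differences grew. A reader might also infer that the plan rules out baseline adjustment. It leaves it unspecified.

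**Conclusion.** The point holds as a low-severity matter of efficiency. The more useful half is the continuous secondary outcomes: naming the baseline value as a covariate cuts the variance by 5 to 27% against follow-up values or by 6 to 22% against change scores over r = 0.3 to 0.7, and settles an open choice. The correlations are assumptions.

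The primary test is valid. It becomes conservative only if sites differ materially: type I error is about 3.3 to 4.4% at assumed site SDs of 0.5 to 0.8 on the logit scale with Satterthwaite df, and lower with cruder df. The size of any gain depends on between-site variation, which the documents do not give, and on how site and group variance are combined. It would be wrong to conclude that the trial is underpowered for this reason: under the planning rates with 20% loss and Satterthwaite df, simulated power stayed at about 90% or above.

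The cluster-retention rule and the baseline visit are a separate validity point, confined to the secondary remission model. They do not touch the primary test.

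**What to change.** 1. **Continuous secondary outcomes:** make cluster-adjusted ANCOVA, with the baseline value and site, the main comparison. Keep the planned t-test or Wilcoxon test as a sensitivity analysis, and state whether it uses follow-up values or changes.
2. **Primary outcome:** use a site-stratified risk difference with the Group-Based cluster variance taken within site. Keep the unstratified cluster-adjusted chi-square as a sensitivity analysis. If a stratification factor is later added to the randomisation, treat it in the same way.
3. **Secondary remission model:** always retain the intervention-cluster random effect, and model post-baseline visits only.

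The cost is analysis-plan wording and some programming, with no new data. Site uses four degrees of freedom, about 0.5 points of primary power if sites do not differ. The change should be made before outcome data are seen by arm.

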Withdrawal from the Trial. This status applies to a participant who is no longer willing to participate in any part of the ELM trial, including group meetings, phone calls, or follow-up visits. However, the participant may allow the trial to use lab and medical data routinely collected by his/her provider.

Withdrawal of Consent. This status applies to a participant who no longer wishes to participate in the trial and declines use of data collected during routine visits with the provider. The status must be requested in writing by the participant and reported to the IRB.

Administrative Withdrawal. This status applies to a participant for whom it is no longer safe for the participant or for the trial staff to continue involvement in the trial. The ELM Safety Committee makes this determination in collaboration with the local site PI. This status terminates all further contact with the participant.

Deceased. This status is assigned once confirmed by the safety committee after review of the adverse event.

RETENTION

Retention has been excellent (90-100%) in the past clinical trials administered by the coordinating center at Rush. However, to assume a conservative approach, the sample size is calculated assuming a 20% loss to follow-up at 24 months. Key strategies to enhance retention include: (1) patient-centered recruitment emphasizing consideration of both the pros and cons of participation, from the participant’s perspective; (2) maintaining 2-3 alternative contacts for each participant at enrollment; (3) same staff member assesses outcomes and maintains regular contact with participant over time; (4) minimization of transportation burden by providing free parking and transportation vouchers; (5) reimbursement for assessment time; (6) reminders about appointments for scheduled intervention and follow-up visits; (7) birthday and holiday cards; (8) collaborative partnerships with providers in participating clinics to enhance their support for their patient’s participation; and (9) negotiating with potential drop-outs to encourage partial withdrawal rather than withdrawal of consent. To reduce

differential drop out, all staff are trained and re-trained to insure equipoise, enthusiasm for a conclusive answer to the question rather than a specific result, and timely response to participant inquiries.

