In the Group-Based arm, the RCU supports the intervention by delivering automatic text messages that are tailored to content presented in the prior week and sent on a pre-existing schedule. At selected group meetings, the RCU prepares personalized feedback reports for each participant. The RCU creates reports on intervention progress assessed as class attendance, weight loss compared to the goal of $\geq 5\%$ loss of baseline body weight, and step count compared to the goal of 10,000 steps on most days. The RCU also creates reports on 3 treatment fidelity measures:

- **Delivery.** Documentation of delivery of specific intervention components;
- **Receipt.** Participant self-reports of acquisition and understanding of specific group content;
- **Enactment.** Participant self-reports of daily vegetable intake, mindfulness habits, and old habit recognition.

These reports are uploaded weekly by the RCU to relevant receivers via the ELM website, including interventionists, participants, investigators, and Intervention Coordinating Unit supervisors.

In the Self-Directed arm, data collected by the Self-Directed Coordinator includes completed telephone calls and frequency of participant-initiated contacts. These data are sent to the RCU and displayed quarterly in aggregate form on the ELM website for review by the Self-Directed Coordinator, investigators, and the ICU supervisors.

Participants in both arms are able to view their own data and track their progress in step counts and weight change. The RCU also tracks frequency of daily log-ons to the ELM website by participants in both arms. **Figure 5** presents the flow of intervention data.

[figure not shown]

Figure 5. Intervention Data Flow

SAMPLE SIZE

The primary outcome of the trial is remission of MetS at 24 months. MetS remission (meeting criteria for <3 MetS components) is clinically relevant and the most common endpoint in MetS trials. Sample size was based upon the assumptions that the chi-square test will be used to compare proportions of participants who remit MetS at 24 months by trial arm, with an overall significance level of 0.05, and power of 85%. This requires a sample size of 117 participants per group, or a total sample size of 234.

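### The secondary mixed logistic model is meant to compare 24-month remission rates, but its usual output is a conditional odds ratio whose meaning is not fixed in advance

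*Combined protocol and SAP*

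**What the plan says.** In the Analysis Plan, the primary analysis compares 24-month remission between arms by a cluster-adjusted chi-square test. The text continues: "A secondary analysis will compare these rates using a mixed effects logistic regression model examining treatment over time". The rates in question are the arms' remission proportions. The model has a treatment-by-time interaction and eight adjustment variables (age, gender, race/ethnicity, socioeconomic status, site, BMI, co-morbidities, number of MetS components) and runs from baseline to 24 months.

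The random part is left to the data: "Random effects (e.g. random intercept, time, intervention cluster) will be included in the model only if they significantly improve model fit", judged by a likelihood ratio test.

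The plan names no effect measure for this model. It does not say whether the effect is conditional or population-averaged, and it describes no step from the fitted model back to remission probabilities by arm.

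**The concern.** The stated purpose is to compare two proportions. The treatment coefficient of a mixed logistic model is a log odds ratio for participants with the same covariates and the same random effects. Odds ratios are non-collapsible. With a participant intercept in the model, the conditional odds ratio lies further from 1 than the odds ratio computed from the arms' rates, even when there is no bias. Each retained set of random effects (none, participant intercept, intercept and slope, intervention group) therefore defines a different quantity for the same pair of rates.

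What is at stake is interpretation. This model is the covariate-adjusted companion to the primary result. An adjusted odds ratio of 4 or 5 printed beside rates of 40% and 20% could be taken for a stronger effect when only the scale differs. The other uses of this outcome (the benchmarks, the effectiveness term of the cost-effectiveness ratio, the dissemination projections) all work with rates.

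**Working it through.** **Inputs from the documents.**
- Rates: 40% and 20%, from the benchmark sentence that begins "The primary hypothesis is achievement of a clinically significant MetS remission at 24 months in" (Analysis Plan).
- Test level and power: two-sided 0.05 and 85%. Sample Size reads "with an overall significance level of 0.05, and power of 85"%.
- Dropout: Retention says that "the sample size is calculated assuming a 20% loss to follow-up at 24 months".
- Cluster ICC: Sample Size cites evidence "indicating that the ICC could reasonably range from 0.01 to 0.20" and adopts 0.15. Clustering is in the Group-Based arm only.

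**Input not in the documents.** The variance between participants on the logit scale. It is assumed below and shown as a range.

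**Step 1: the plan's own figure.** The standard two-proportion formula is n = [1.960·√(2·0.3·0.7) + 1.036·√(0.4·0.6 + 0.2·0.8)]² / 0.2² = 92.7, so 93 per arm. Dividing by 1 − 0.20 gives 116.25, so 117. This matches the stated 117 per group and confirms that 40% against 20% is the design contrast.

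**Step 2: odds ratio from the rates.** (0.4/0.6) / (0.2/0.8) = 2.67.

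**Step 3: conditional odds ratio for the same rates.** Take a normal participant intercept with variance σ² = [ICC/(1 − ICC)]·π²/3. For each arm, solve numerically (Gauss-Hermite quadrature) for the logit η at which the average of 1/(1 + exp(−η − b)) over b ~ N(0, σ²) equals that arm's rate. The conditional odds ratio is exp(η for 40% − η for 20%).

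| Assumed latent ICC | σ | η for 40% | η for 20% | Conditional odds ratio | Multiple of 2.67 |
|---|---|---|---|---|---|
| 0.2 | 0.91 | −0.476 | −1.607 | 3.10 | 1.2 |
| 0.4 | 1.48 | −0.569 | −1.905 | 3.80 | 1.4 |
| 0.6 | 2.22 | −0.713 | −2.377 | 5.28 | 2.0 |
| 0.8 | 3.63 | −1.022 | −3.399 | 10.77 | 4.0 |

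On the 0/1 scale these rows correspond to between-visit correlations of about 0.11–0.15, 0.24–0.28, 0.39–0.43 and 0.57–0.60. The multiple reaches 2 at σ = 2.24 (latent ICC 0.60) and 3 at σ = 3.06 (latent ICC 0.74).

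**Step 4: the cluster effect alone.** Put a random effect in the Group-Based arm only and leave the other arm at logit(0.20) = −1.386. With the documents' ICC of 0.01 to 0.20 read on the 0/1 scale, the conditional odds ratio runs from 2.66 down to 2.41, or 1.00 to 0.90 times the figure from the rates. If the effect is wrongly placed in both arms, the multiple is 1.01 to 1.25.

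**Step 5: does the likelihood ratio test matter?** A small simulation used 600 participants, three follow-up visits, no covariates and 12 runs per setting. Median fitted 24-month odds ratios with and without the participant intercept were 3.26 and 2.74 (σ = 1), 5.27 and 2.86 (σ = 2), and 8.16 and 2.72 (σ = 3). The smallest likelihood ratio statistic for the intercept was 20, so the test kept it in every run.

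**The case against.** The strongest reply is that the plan never promises an odds ratio. It promises a comparison of rates, and fitted 24-month probabilities can be taken from this same model. That is fair: the fault is an effect measure left unstated, not a commitment to the wrong one. The conditional odds ratio is only the usual output.

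A reader might infer that the reported effect will be several times too large. The documents do not support that. A multiple near 4 needs an assumed latent ICC of about 0.8, and no within-participant variance is given. The one variance figure they do give, the cluster ICC, moves the odds ratio slightly towards 1 when placed in the clustered arm.

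A reader might also blame the likelihood ratio test for the gap. The simulation does not bear this out: where the gap is large, the intercept is retained. The test leaves the meaning of the estimate open, but the size of the gap comes from the conditional scale.

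It can also be objected that Step 3 is not the plan's model. It uses one time point and no covariates, whereas the plan's model starts at baseline, when eligibility requires every participant to have metabolic syndrome. The actual gap could therefore differ. A small fit run from baseline with linear time still gave odds ratios of about 3.6 to 4.6, so the gap does not vanish, but the table is an indication and not a forecast.

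Finally, the achieved rates will be shown against the benchmarks in any case, so a careful reader has the means to avoid the misreading. That limits the importance of the point without removing it.

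**Conclusion.** The point holds as a modest improvement. The secondary model is described as comparing rates, but its default estimate does not target them, and the quantity estimated depends on a test applied to the trial data. At 40% against 20%, the conditional odds ratio would be about 3.1 to 5.3 where the rates give 2.67. This assumes a normal participant intercept with latent ICC between 0.2 and 0.6, no covariates and a single time point. Higher figures need stronger persistence, which may or may not be present.

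It would be wrong to infer bias, an inflated type I error or any weakness in the primary result. Non-collapsibility changes the scale of an effect and does not make it false, and the cluster-adjusted chi-square test compares the rates directly.

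**What to change.** - **Reported result.** From this model, report the standardised 24-month remission probability in each arm and their difference with a 95% CI, averaged over the covariates and integrated over the random effects. Give the conditional odds ratio as a supporting figure.
- **Random effects.** Pre-specify them as a participant intercept and an intervention-group effect in the Group-Based arm, in place of selection by test. Standardisation settles only the scale: if the test drops the group effect, the model-based interval ignores clustering.
- **Time.** Treat visit as categorical so that a linear trend does not distort the 24-month probabilities. By eligibility nobody is in remission at baseline, so a baseline category cannot be estimated. The outcome rows should be the three follow-up visits, with baseline information entering as covariates.

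A population-average logistic model with small-sample cluster-robust variance would also target the rates. It is a trade-off: unweighted, it generally needs stronger missing-data assumptions than a likelihood-based mixed model, which matters when 20% loss is planned for.

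The cost is some SAP wording, one post-estimation step and a little more analysis work. The secondary effect will also look smaller than the conditional odds ratio. Data collection, sample size and the primary analysis do not change.
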